The response to targeted biologic therapies is heterogeneous despite the use of biomarkers to select potential responders. Unfortunately, even when patients with a high likelihood of response are selected, 10-15% have complete non-response in all clinical parameters, 40% have a robust and complete response to therapy, and the remainder of patients have a partial response. This is likely related to the presence of overlapping inflammatory pathways, co-morbid eosinophilic diseases that affect response to therapy, possible sub-optimal dosing of drug, and the lack of highly specific biomarkers.

Little is known about how biologics impact the use of inhaled asthma therapies and whether the heterogeneity in responses to biologics could be partially attributed to nonadherence with maintenance therapies once biologic therapy is initiated. Data collection on use of both maintenance and inhaled therapies is based primarily on patient self-reporting. The Digihaler™ presents a unique opportunity to gain invaluable insights into both patterns of use of inhaled therapies and changes in inspiratory flow parameters in patients with severe asthma who are treated with biologics. In addition, coupling the maintenance and rescue Digihaler™ will allow the collection of a significant amount of information both about baseline therapies and exacerbations. Furthermore, the granular data collected from these inhalers will be invaluable in determining the impact of inhalation parameters on predicting asthma outcomes and in determining whether these measurements can serve as surrogates of expiratory flow measurements that are the cornerstone of asthma management but often challenging to obtain in real world settings. Coupling digital biomarkers from the inhaler with biological and clinical characteristics in a cohort of severe asthma patients will lead to an enhanced ability to not only understand the impact of

maintenance therapies on asthma outcomes but will also provide us with the opportunity to use machine learning algorithms to develop predictive models that may enhance our ability to predict response to biologics.

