9.2 SAMPLE SIZE DETERMINATION

Sample size calculations were based on peak inspiratory flow measurements.

Based on population-based estimates of peak inspiratory flow:

<https://www.ncbi.nlm.nih.gov/pmc/articles/PMC5328129/> The mean was 115 and standard deviation was 15. With a 100-patient sample, 95% CI of our estimate of the mean would be plus or minus 3, e.g. 115 (95 CI 112 – 118).

The machine learning model will be performed based on the most common measure to evaluate performance which is discrimination that is assessed by an AUROC. If we have a 100-patient sample and assume a 50% event rate (<http://www.biosoft.hacettepe.edu.tr/easyROC>), we would have adequate power to conclude that a model with an AUROC performance of > 0.65 has confidence intervals that won't cross 0.5 (which would be a model that is no better than chance).

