9.4.3 ANALYSIS OF THE SECONDARY ENDPOINT(S)

1. To develop an algorithm that can identify probable imminent exacerbation events using Digihaler™ inhalation parameter measurements, we will compare the performance of several different machine learning regression models. Since we expect our training set to be relatively small with a low event rate, we plan to use the entire inhalation parameter dataset for model training but will employ repeated k-fold cross-validation to reduce variance (over-fitting) and include non-linear features to reduce bias (under-fitting). Examples of features that could be computed and included in this model include but are not limited to: difference between current value and patient-specific 7-day moving average, difference between current value and patient-specific 24-hour moving average, 7-day sample entropy, 24-hour sample entropy, difference in Min-Max over last 24 hours, etc.

A logistic regression model would treat the outcome (exacerbation) as a binary (Yes/No) event. The output of this model would be a daily probability between 0 and 1 that an exacerbation event will occur within a certain period of time. Different models will be fit for different periods of time (e.g., 24, 48, 72 hours) and the performance of each model assessed and compared to others. A recurrent event survival model would treat the exacerbations as discrete events in time. The output of this model would be the predicted time (e.g., in decimal days or hours) until the next event. Other models may include convolutional and/or recurrent neural networks (RNN) with LSTM or GRU architecture with varied numbers of hidden layers.

2. To determine whether and how PIF is associated with FEV1 and FVC, we assess the linearity and strength of the relationship using scatter plots, calculate the paired correlations (Pearson, Kendall, and Spearman), and compute univariate linear regression equations with PIF as the predictor and FEV1 or

FVC as the response. If non-linearity is found, we will determine the appropriate PIF transformation or polynomial term to use in the regression. Regression summary statistics (e.g., R-squared, Mean Absolute Error, Coefficients, and p-values) will be reported.

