3. Patients will be assigned to one of three adherence groups (low, moderate, high) based on Digihaler™ inhalation usage parameters over the previous month. We will use the Chi-squared test to determine if group differences exist for each asthma outcome over the next month, and Tukey's Honest Significant Difference test to determine which groups are significantly different.

4. Patients will be assigned to one of three biologics response groups (non, partial, complete) based on six asthma factors (described earlier). We will use the Chi-squared test to determine if group differences exist for each inhalation parameter, and Tukey's Honest Significant Difference test to determine which groups are significantly different.

5. To develop an algorithm that can predict patients that will respond to biologics regression or classification models. Since we expect our training set to be relatively small with a low event rate, we plan to use the entire inhalation parameter dataset for model training but will employ repeated k-fold cross-validation to reduce variance (over-fitting) and include non-linear features to reduce bias (under-fitting). We do not know a priori whether regression or classification would be the appropriate approach to this question so we will test models using both approaches. The classification approach can be formulated as either a two-class problem – Non vs. Partial or Complete responders, or Non or Partial vs. Complete responders – or a three-class problem – Non vs. Partial vs. Complete. The regression approach requires a two-class formulation using logistic regression. Different models will be fit for different formulations and the performance of each model assessed and compared to others.

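### Cross-validation as planned does not control over-fitting in a logistic model fitted to all the data, and no calibration check would reveal over-extreme probabilities

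*Combined protocol and SAP*

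**What the plan says.** Section 9.4.3 describes two prediction tasks: imminent exacerbations (item 1) and response to biologics (item 5). Both items say the training set will be small with few events, that all of it will be used for training, and that the analysts "will employ repeated k-fold cross-validation to reduce variance (over-fitting) and include non-linear features to reduce bias (under-fitting").

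For the logistic version of item 1, "The output of this model would be a daily probability between 0 and 1". In item 5, "The regression approach requires a two-class formulation using logistic regression", alongside two- and three-class classifiers. Item 1 also names a recurrent-event survival model and neural networks. Section 9.4.9 adds feature selection, with no method given.

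On performance, Section 9.2 relies on "the most common measure to evaluate performance which is discrimination that is assessed by an AUROC". The synopsis (exploratory endpoint 11) and the Section 3 table add a confusion matrix, described on the training dataset, from which accuracy, sensitivity and specificity are to be computed. Calibration intercept, slope, plot and Brier score do not appear. Nor do a penalty, shrinkage, a tuning parameter, a hold-out set or a limit on the number of predictors.

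**The concern.** Cross-validation refits a model on parts of the data and scores it on the rest. That gives a more honest estimate of performance, or a way to choose a penalty or a level of complexity. It does not change the final logistic model fitted to everyone. With no tuning target named, the safeguard as written leaves over-fitting where it was, while the added non-linear features increase it.

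An over-fitted logistic model gives probabilities that are too close to 0 and 1. AUROC depends only on ranking, and a confusion matrix only on one cut-off, so neither shows whether a stated 80% means 80%. A confusion matrix on the training data also flatters the model. Sections 2.1 and 4.1 hope that such models will eventually support early detection of exacerbations and early judgements about a biologic. For that, the stated probability has to be trustworthy, or its error has to be visible.

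**Working it through.** **The plan's own figure.** Section 9.2 says: "If we have a 100-patient sample and assume a 50% event rate", a model with AUROC above 0.65 "has confidence intervals that won't cross 0.5". By Hanley-McNeil with A = 0.65 and 50 against 50:
- Q1 = A/(2−A) = 0.481 and Q2 = 2A²/(1+A) = 0.512.
- Variance = [0.2275 + 49(0.481−0.4225) + 49(0.512−0.4225)]/2500 ≈ 0.0030, so SE = 0.055.
- 95% CI = 0.543 to 0.757.

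The claim reproduces, but it concerns discrimination only. (At 10 or 15 events per 100 the interval is 0.457 to 0.843 or 0.489 to 0.811, which is a separate point.)

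**Does cross-validation alter the fit?** A logistic model was fitted to all the data before and after repeated 10-fold cross-validation. The largest coefficient difference was 0.

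**How extreme could an unpenalised fit be?** Inputs from the documents are n = 100 and the response shares in Section 2.1: "10-15% have complete non-response in all clinical parameters, 40% have a robust and complete response to therapy". The number and strength of predictors are not given, so they are assumed and varied. The calibration slope is the coefficient when the outcome in new patients is regressed on the model's linear predictor. It is 1 if right and below 1 if predictions are too extreme.

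Set-up A: linear-predictor SD 1; with 20 features, five carry the signal. Set-up B: independent features of equal strength, true AUROC 0.65 / 0.75, 100 data sets per setting. Median slopes, unpenalised (ranges are across separate runs):

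| Features | A, 40% events | A, 15% events | B, 40% events | B, 12.5% events |
|---|---|---|---|---|
| 1 | – | – | 0.96 / 0.98 | 0.92 / 1.03 |
| 3 | 0.82–0.87 | 0.78–0.81 | 0.73 / 0.81 | 0.52 / 0.73 |
| 5 | 0.72 | 0.66 | 0.59 / 0.72 | 0.37 / 0.60 |
| 10 | 0.54 | 0.38 | 0.33 / 0.55 | 0.17 / 0.34 |
| 20 | 0.29–0.31 | 0.15 | 0.17 / 0.30 | 0.06 / 0.11 |

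**What a slope means.** Take the calibration intercept as 0. A stated 90% has logit ln 9 = 2.197. With slope 0.54 the true logit is 1.186, or about 77%. With slope 0.29 it is 0.637, or about 65%.

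**Would the planned outputs show it?** In set-up B (12.5% events, 10 features, AUROC 0.65), 40% of new patients get a prediction below 0.05 or above 0.95, against 6% in truth. AUROC is 0.80 on the training data and 0.58 in new patients. A training-data confusion matrix comes from the same flattering predictions.

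**Daily model (item 1).** 100 patients × 365 days = 36,500 patient-days. With an assumed 0.5 to 2 exacerbations per patient-year (50 to 200 events) and AUROC 0.65, median slopes are 0.86–0.97 with 5 features, 0.42–0.79 with 20 and 0.21–0.59 with 50. There were six data sets per setting, and days were treated as independent, which is optimistic. At 20 features this is milder than the 0.17 for the 40% response model in set-up B.

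**With a penalty.** Ridge tuned by cross-validation gives median slopes of 0.97–1.15 in set-up A and 0.88–1.45 in set-up B, with similar AUROC (for example 0.60 either way at 40% events, 10 features, AUROC 0.65). The spread stays wide: in that setting the median is 1.34 with interquartile range 0.72–3.19.

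**The case against.** The tempting stronger reading is that the probabilities will be far too extreme. The documents do not support that. They give no number of predictors, and with one to three the slope ranges from about right to moderately low. They neither name nor exclude a penalty. Section 9.4.9 plans feature selection and scaling, and items 1 and 5 compare several models. If cross-validation is meant to choose complexity, it would limit over-fitting. The absence of a calibration check also does not cause extreme predictions; it leaves them unseen.

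Other limits are fair. Item 5 never promises a response probability as its output, and classification is planned beside logistic regression. The simulations say nothing about the survival or neural-network models. Both algorithms are exploratory endpoints in the synopsis, Section 2.1 leaves clinical utility to future trials, and nothing in this study acts on a prediction.

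What stands is that the plan gives cross-validation a job it cannot do as described, and offers no measure of whether a probability is right. Ten or more features is also not far-fetched. Sections 8.1.2.1, 8.1.2.2 and 8.1.2.6 list roughly 12 history items, five biological or lung-function items and three questionnaires, or about 20 possible candidates. For item 1, four inhaler measurements times the five example features makes 20 per inhaler. These are variables collected or exemplified, not a stated predictor list.

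**Conclusion.** The point holds in conditional form. As written, repeated k-fold cross-validation does not reduce over-fitting in a logistic model fitted to all the data, and no calibration measure is planned although item 1 outputs a probability. If that model is unpenalised with about 10 or more candidate features at n = 100, its predictions would be much too extreme: median slope about 0.5 or lower with 10 features and roughly 0.15 to 0.3 with 20, at 40% and 15% events. The planned outputs would not show this. With 3 features the slope is about 0.8 to 0.9 in set-up A, and 0.52 to 0.81 in set-up B.

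These sizes rest on assumed feature counts, independent features and assumed signal strength. A reader might infer that the daily model is equally affected or that every planned model is. The first is not supported, since its slopes are higher for the same number of features and depend on the assumed event count. The second was not examined. This should be corrected before analysis, but it does not touch the descriptive primary endpoint.

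**What to change.** In Section 9.4.3, items 1 and 5:
- State that cross-validation is used for tuning and for estimating performance, with folds split by patient so that one patient's days never fall in both training and test parts.
- Fit the logistic models with a penalty tuned in those folds, for example ridge or elastic net.
- Report AUROC and the confusion matrix from out-of-fold predictions rather than the training data. For any model presented as a probability, add calibration intercept, slope and plot. Give intervals for all of these.

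Do not add a rule that withholds probabilities when the slope interval excludes 1. With 20 features, ridge slopes had interquartile ranges of 0.76–2.33 (40% events) and 0.65–2.35 (15%), yet such a rule rejected only 7% and 17% of those models, because intervals at n = 100 are too wide to screen with.

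The cost is plan wording and standard R functions, with no new data. Penalised coefficients have no simple p-values. Calibration at n = 100 stays imprecise even with a penalty, which is why the intervals must be shown.

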9.4 STATISTICAL ANALYSES

9.4.1 GENERAL APPROACH

We will perform a retrospective analysis of prospectively enrolled patient data. Following completion of the study's data collection period, data from the Digihaler™ asthma inhalers will be downloaded to secure servers, joined to clinical data from the electronic medical record (including exacerbation event data) and patient questionnaire responses, and analyzed using R statistical analysis software. The University of Michigan Morphomics Analysis Group will collaborate with the TEVA analytics team to produce a rigorous and reproducible research result. An alpha level of 0.05 will be used to determine "statistical significance" with a Bonferroni correction ($\alpha / \# \text{ tests}$) applied to account for multiple testing when appropriate.

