9.4.9 EXPLORATORY ANALYSES

We plan to conduct extensive exploratory analyses including but not limited to: data cleaning and aggregation, outlier analysis, multicollinearity (correlation) analysis, sex effect analysis, age effect analysis, time series analysis, unsupervised cluster analysis, univariate testing (T-tests, Fisher's Exact Test, Wilcoxon Test, Chi-Squared Test, Tukey's Honest Significant Difference (HSD) Test), multivariable linear and non-linear regression, feature creation and selection for machine learning models, feature scaling and centering, training machine learning models using repeated k-fold cross-validation, and extensive data visualization for correlations and time series analysis.

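### Models and features are compared on the same patients with plain k-fold cross-validation only, so the cross-validated AUROC of whatever is chosen is biased upward, by an amount the plan leaves open

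*Combined protocol and SAP*

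**What the plan says.** Section 9.4.3 item 1 (exacerbations) states that "we will compare the performance of several different machine learning regression models". It names logistic, recurrent-event and neural-network models, gives 24, 48 and 72 hours as example windows, and offers a feature list that is explicitly not exhaustive.

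Item 5 (response to biologics) tests regression and classification under two two-class splits and one three-class problem: "Different models will be fit for different formulations and the performance of each model assessed and compared to others". Both items train on all the inhalation data and rely on repeated k-fold cross-validation, with the number of folds and repeats not given.

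Section 9.4.9 lists univariate testing and, further on, "feature creation and selection for machine learning models, feature scaling and centering, training machine learning models using repeated k-fold cross-validation".

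The only numerical benchmark is in section 9.2 (repeated in 4.2): with 100 patients and 50% events, "a model with an AUROC performance of > 0.65 has confidence intervals that won't cross 0.5".

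The documents give no hold-out set, nesting, patient-level split, fixed candidate list, selection rule, optimism correction or validation cohort. The Bonferroni rule in 9.4.1 is for multiple tests, where appropriate, and does not address an AUROC that was picked because it was high.

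**The concern.** Cross-validation gives a fair estimate for one procedure fixed in advance. If the features, the model or the formulation are picked by looking at the same patients, the figure for the winner carries the luck that made it win. This remains true when every prediction is out of fold.

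The stake is a published predictor of biologic response or of exacerbations whose apparent discrimination is partly or wholly selection, and which fails in the next cohort. Section 9.1 lists both predictions as hypotheses to test, and section 4.1 hopes that such algorithms will inform whether a biologic is continued.

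**Working it through.** **Inputs from the documents.** 100 patients and 50% events (9.2); benchmark AUROC 0.65 with an interval excluding 0.5 (9.2, 4.2); alpha 0.05 (9.4.1), taken as a two-sided 95% interval; non-response 10-15% and complete response 40% (2.1).

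**Assumptions, because the plan gives no figures.** 20, 40 or 80 candidate features with five kept; 10 folds; 12 competing models with pairwise correlation 0.3 to 0.8.

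**1. The plan's own figure.** Hanley-McNeil with A = 0.65, a = A/(2-A) = 0.4815, b = 2A²/(1+A) = 0.5121, A² = 0.4225 and n1 = n0 = 50:

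SE² = [A(1-A) + 49(a-A²) + 49(b-A²)]/2500 = (0.2275 + 2.890 + 4.391)/2500 = 0.00300, so SE = 0.0548.

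95% CI = 0.65 ± 1.96 × 0.0548 = 0.543 to 0.757. The figure reproduces. At 50/50, any AUROC from about 0.61 has an interval above 0.5.

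**2. One pre-specified model, no signal.** Null SE = √[(n1+n0+1)/(12·n1·n0)].
- 50 events: √(101/30000) = 0.0580; z = 0.15/0.0580 = 2.585; P(AUROC ≥ 0.65) = 0.5%.
- 12 events: √(101/12672) = 0.0893; z = 1.68; P = 4.7%.

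**3. Best of 12 null models, no feature screening.** With common correlation ρ, P(max ≥ z) = 1 - ∫ Φ((z-√ρ·u)/√(1-ρ))¹² φ(u) du.

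| Criterion | one model | ρ = 0.8 | ρ = 0.3 |
|---|---|---|---|
| 95% CI above 0.5 (z = 1.96) | 2.5% | 9.3% | 20.2% |
| AUROC ≥ 0.65, 50% events | 0.5% | 2.3% | 4.9% |
| AUROC ≥ 0.65, 40% events | 0.6% | 2.6% | 5.7% |
| AUROC ≥ 0.65, 12% events | 4.7% | 15.3% | 32.4% |

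The last row concerns the 0.65 mark alone. With 12 events the Hanley-McNeil interval at 0.65 is 0.472 to 0.828, so that AUROC would not also exclude 0.5.

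**4. Feature screening before or inside the folds.** Simulation of pure noise: 100 patients, 50% events, top five features by t-test, logistic model, 10-fold cross-validation, 400 data sets per setting.

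| Candidate features | Screened on all data: mean AUROC; share > 0.65 | Screened inside folds: mean AUROC; share > 0.65 |
|---|---|---|
| 20 | 0.63; 33% | 0.50; 3% |
| 40 | 0.67; 71% | 0.50; 4% |
| 80 | 0.71; 96% | 0.50; 4% |

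Repeats with other random seeds gave 28-38%, 62-73% and 91-96% outside the folds, and 2-5% inside.

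**5. Does nesting cure it?** A second simulation used 40 noise features and 20 candidates (four feature sets × five model types), with eight features chosen inside the folds and 5-fold cross-validation repeated five times.
- Best of 20, not nested (400 data sets): AUROC ≥ 0.65 in 4.8%, 9.0% and 27.8% of runs at 50%, 40% and 12% events. Choosing across both two-class splits (40 candidates): 34.7%.
- Same candidates, nested 5 × 5 (150 data sets): mean AUROC 0.50 at each rate; ≥ 0.65 in 1.3%, 1.3% and 5.3%.

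**Limit.** These runs use one binary outcome per patient, as in item 5's two-class versions. They do not size the effect for item 1's daily predictions, the recurrent-event model or the three-class problem. The direction of the bias is the same there.

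**The case against.** Three stronger readings are tempting, and the documents do not support them.

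- A reader might infer that features and models are chosen on all the data. The plan does not say so. Section 9.4.9 is an open-ended list, not a sequence of steps, and nothing states that the univariate tests screen model features. The plan is silent on whether selection lies inside the folds, so the 30-95% figures are conditional.
- A reader might infer that an AUROC above 0.65 counts as success. Sections 4.2 and 9.2 use it as a sample-size statement for one model, and 9.4.3 sets no performance threshold.
- A reader might infer that the winner's cross-validated AUROC will be the headline. Item 5 says only that models are assessed and compared. That such a figure would be reported is inferred from the absence of any other data. For the exacerbation algorithm, the synopsis and section 3 do name a confusion matrix on the training dataset; that is a separate matter.

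The defence can add that the synopsis lists both algorithms as exploratory endpoints (although 9.1 and 9.4.3 place them under secondary), and that section 2.1 leaves tests of clinical utility to future trials. With selection inside the folds and 50% events, noise seldom reaches 0.65.

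All this limits the size and the stakes. It does not remove the defect: a comparison of this breadth with plain cross-validation gives no unbiased performance figure for whatever is chosen. The mild case also depends on 50% events, whereas section 2.1 cites 10-15% non-response and items 1 and 5 themselves expect a low event rate.

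**Conclusion.** The concern holds in conditional form. The direction of the bias is certain for any model or feature set chosen on the patients used to score it. Its size is not fixed by the plan.

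Under the stated assumptions, it is large if features are screened before cross-validation. If only the best model is picked, it is modest at 50% events: the 0.65 mark is rarely reached, but the chance of an interval above 0.5 is about four to eight times nominal (9.3/2.5 and 20.2/2.5). At event rates near the cited non-response rate, it is again material for the 0.65 mark. The plan should be changed, because a better method is available without new data.

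**What to change.** In 9.4.3 items 1 and 5, replace plain repeated k-fold cross-validation with nested cross-validation in which all records of a patient stay in the same fold. Feature selection, scaling, tuning and model choice should take place within the inner loop, using the outer training patients only. An optimism-corrected bootstrap of the whole procedure is an acceptable alternative.

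Report the outer-loop performance, with its interval, as the result. Show the performance of every model, horizon and formulation compared, and label the outcome as model development that needs external validation. Naming one main formulation and one main horizon in advance would help, but it is an option and not the only remedy.

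The cost is computing time, some SAP wording and a lower reported AUROC. With few events the outer-loop estimate will also be imprecise (12 events over five folds is 2.4 per fold). No extra patients or visits are needed.
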